6. BIOSTATISTICAL ANALYSIS

6.1 Primary endpoint definition

The primary endpoint is the **incidence of postoperative AKI**, defined according to the KDIGO criteria as any of the following: urine output <0.5 ml/kg/h for ≥ 6 consecutive hours (assessed within the first 48h or until the Foley catheter is removed, whichever occurs first; an increase in SCr ≥ 0.3 mg/dl within the first 48h; an increase in SCr $\geq 50\%$ within the first 7 days; or receipt of RRT within the first 7 days.⁸⁵ The immediate preoperative SCr will be used as the baseline value for all analyses. SCr is measured at least once daily for routine clinical care postoperatively. Assessment of urine output monitoring will begin at the start of surgery.

6.2 Statistical analysis for the primary endpoint

Hypothesis 1: DFO will reduce the incidence of postoperative AKI. We will use the χ^2 test to compare the proportion of patients in the DFO versus normal saline (placebo) group who develop the primary endpoint. We will perform sensitivity analyses to assess the composite outcome of AKI or death, since death is a competing risk for AKI. We will use logistic regression to assess for heterogeneity of therapeutic response to DFO across the following subgroups: age; sex; race (White vs. non-White); preoperative eGFR (<60 vs. ≥ 60 ml/min/1.73m 2); AKI risk score (≤ 8 vs. >8); duration of CPB (<120 vs. ≥ 120 min; <120 vs. 120-180 vs. >180 min)); intraoperative RBC transfusion; and type of surgery (elective vs. urgent/emergent).

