3. SUBJECT SELECTION

3.1 Inclusion criteria (each of the following)

1. Age ≥ 18 years
2. Undergoing coronary artery bypass graft (CABG) and/or valve surgery with CPB. Includes combination surgeries that involve CABG and/or valve plus other procedures (e.g., Maze procedure, aortic aneurysm repair)
3. AKI risk score ≥ 6 at the time of screening (Table 4)
4. Written informed consent from the patient or surrogate

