3.3 Source of subjects

Patients scheduled to undergo cardiac surgery at BWH, MGH, and BIDMC, all located in Boston, MA.

Table 4. Risk factors for cardiac surgery-associated AKI

Risk Factor	Points
Male sex	1
eGFR (ml/min/1.73m ²)*	
45-59	1
30-44	2
<30	3
Hemoglobin (g/dL)*	
10-11.9	2
<10	4
WBC count (per mm ³)*	
<4	1
>12	2
Platelet count (10 ⁹ /L)*	
<150	1
>400	2
Albumin (g/dL)*	
3.6-4.0	1
<3.6	2
Hypertension	1
Diabetes mellitus	1
CHF†	1
Chronic liver disease‡	1
Prior cardiac surgery	2
Combined CABG/valve	1

*Closest value in the last 3 months.

†Any of the following: CHF; HFrEF; HFpEF; NYHA class III or IV; diastolic dysfunction; or LVEF $\leq 40\%$.

‡Any of the following: chronic liver disease; cirrhosis; NAFLD; AIH; chronic viral hepatitis.

Abbreviations: AIH, autoimmune hepatitis; CHF, congestive heart failure; eGFR, estimated glomerular filtration rate (assessed using CKD-EPI equation); HFpEF, heart failure with preserved ejection fraction; HFrEF, heart failure with reduced ejection fraction; LVEF, left ventricular ejection fraction; NAFLD, non-alcoholic fatty liver disease.

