4.3 Treatment assignment and randomization

Participants will be randomly assigned in a 1:1 fashion to receive DFO or an equal volume of normal saline. Randomization will be stratified by site and by preoperative eGFR (<60 vs. ≥ 60 ml/min/1.73m²) at the time of screening. Treatment assignment lists will be generated centrally by the study biostatistician, [name] PhD, using permuted block sizes of 4 and sent to the research pharmacies at each site. Patients, physicians, nurses, and study investigators will be blinded to treatment assignment.

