6.3 Sample size and power

Based on our preliminary data and prior studies,^{37, 38} the anticipated AKI event rate in the placebo group is **50%**. We hypothesize the AKI event rate in the DFO group will be **34%**, an effect size that has been proposed to be reasonable for studies in AKI.^{86, 87} A total of 296 patients ($n=148$ per group) will provide 80% power to detect the above treatment effect, with a two-sided α of 0.05. Enrollment of 330 patients provides a small buffer for potential early withdrawal from the study, which we anticipate will be uncommon due to the nature of the study (inpatient and short duration).

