6.6 Modified intention-to-treat analysis

The final analysis will be limited to patients who are initiated on the study drug, irrespective of whether they are able to complete the entire 12h infusion, consistent with a modified intention-to-treat analysis. Patients who consent but are subsequently found to be ineligible prior to initiation of the study drug infusion (e.g., if a patient develops a new fever several hours prior to surgery) will be withdrawn. In such cases, the reason for the withdrawal will be documented and reported, but these patients will not be included in the final analysis, nor will they count toward the total enrollment target of 300 analyzable patients. Accordingly, we anticipate enrolling up to 330 patients (10% buffer) to obtain 300 analyzable patients, accounting for withdrawal prior to receipt of study drug.

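### The primary χ² test is valid and meets its planned power, but using the randomisation strata and the baseline AKI risk score could add up to about 5 points of power with no extra patients

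*Combined protocol and SAP*

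**What the plan says.** Section 6.2 names one primary analysis, a χ² "test to compare the proportion of patients in the DFO versus normal saline (placebo) group who develop the primary endpoint". Its sensitivity analysis changes the outcome to AKI or death and adds no covariates. Baseline variables appear only in the subgroup plan: "We will use logistic regression to assess for heterogeneity of therapeutic response to DFO across the following subgroups", a list that includes eGFR split at 60 and the AKI risk score split at 8.

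Section 4.3 states: "Randomization will be stratified by site and by preoperative eGFR", with eGFR cut at 60, 1:1 allocation and permuted blocks of 4. Three sites and two eGFR groups make six strata. Section 3.1 requires a score of at least 6 from Table 4 at screening, so each patient is scored before treatment.

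Section 6.3 assumes AKI in 50% on placebo and 34% on deferoxamine, and says that 296 patients (148 per group) "will provide 80% power to detect the above treatment effect" at two-sided 0.05. Section 6.6 says "we anticipate enrolling up to 330 patients (10% buffer) to obtain 300 analyzable patients".

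No adjusted primary analysis appears anywhere else in section 6.

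**The concern.** The design treats site and eGFR as important enough to balance, and the risk score as important enough to decide entry. The primary test then ignores all three. A test that ignores prognostic randomisation strata tends to be somewhat conservative. The score is not a stratification factor, so leaving it out affects precision and not validity.

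Efficiency is what is at stake. The plan has little margin: 300 analysable patients against 296 required. If the strata and score predict AKI among enrolled patients, the same 300 patients can give higher power and a narrower confidence interval, which would also help in planning the phase 3 trial that section 8.2 foresees.

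**Working it through.** **1. Reproduce the plan.** Inputs from section 6.3: p₁ = 0.50, p₂ = 0.34, two-sided α = 0.05. The difference is 0.16 and the mean rate is 0.42.

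Power = Φ[(0.16 − 1.96·SE₀)/SE₁], with SE₀ = √(2·0.42·0.58/n) = √(0.4872/n) and SE₁ = √((0.50·0.50 + 0.34·0.66)/n) = √(0.4744/n).

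- n = 148 per arm: SE₀ = 0.0574, SE₁ = 0.0566, Φ(0.840) = 79.9%.
- n = 150 per arm (section 6.6): SE₀ = 0.0570, SE₁ = 0.0562, Φ(0.859) = 80.5%.

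The stated 80% holds.

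**2. Effect of adjustment by formula.** If the covariates explain a share R² of the outcome variance, both standard errors shrink by √(1 − R²). R² is an assumption, because the documents give none.

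| R² (assumed) | Power, 150 per arm | Reduction in standard error |
|---|---|---|
| 0 | 80.5% | 0% |
| 0.02 | 81.3% | 1.0% |
| 0.05 | 82.5% | 2.5% |
| 0.10 | 84.4% | 5.1% |
| 0.12 | 85.2% | 6.2% |

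**3. Simulation of the actual design.** There were 300 patients, with permuted blocks of 4 in six strata and marginal AKI rates of 50% and 34%. Each setting had 20,000 runs. Assumed inputs were three sets of prevalences for the Table 4 items, a site split of 40/35/25, and four levels of prognostic strength. The score was built from Table 4 and patients were kept only if it was at least 6. That selection cut the score's standard deviation from 2.17–2.43 to 1.41–1.64, and the mean score gap between eGFR groups from 1.53–1.64 to 0.43–0.67 points.

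The first results column gives the range over the three prevalence sets. The second gives power in the middle set for χ², Cochran-Mantel-Haenszel (CMH) on the strata, and logistic regression on strata plus score.

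| Assumed prediction (AUC) | Change in power, strata plus score vs χ² | χ² / CMH / logistic, middle set (%) |
|---|---|---|
| None (0.50) | −0.4 to −0.2 points | 80.7 / 80.3 / 80.3 |
| Weak (0.56) | −0.1 to +0.2 | 81.5 / 81.1 / 81.5 |
| Moderate (0.62–0.63) | +1.1 to +1.5 | 81.3 / 81.2 / 82.6 |
| Strong (0.70–0.72) | +4.0 to +4.8 | 81.8 / 82.7 / 86.1 |

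- The Monte Carlo standard error of a change is at most 0.19 points.
- In the middle set, moderate corresponds to AKI of 55% versus 44% by eGFR group, and strong to 60% versus 39%.
- Using the strata alone (CMH) changed power by −0.5 to +1.0 points.
- The confidence interval for the risk difference was about 2% narrower (moderate) or 6 to 8% narrower (strong).
- The standardised risk difference test matched the logistic test within 0.1 points.
- Type I error was 4.7 to 5.7% for χ² over the 12 settings, and 4.6 to 5.4% for the standardised risk difference.

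**4. Cross-check.** A second simulation used a different score distribution and different covariate effects, with 148 per arm and 4,000 runs (error about 0.6 points on each power figure). From χ² to standardisation on strata plus score, power went from 82.0% to 81.8% (no prediction), 81.0% to 83.3% (AUC 0.65) and 80.6% to 85.2% (AUC 0.70). Strata alone gained 0.4 points or less.

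**5. In patients.** On the step 1 formula, 154 and 156 per arm give 81.5% and 82.0% (+1.0 and +1.5 points over 150). 167 and 171 per arm give 84.5% and 85.3% (+4.0 and +4.9). The moderate gain is therefore worth about 8 to 12 patients in total, and the strong gain about 34 to 42.

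**The case against.** **The plan is not wrong.** A prespecified, valid test with the power it was sized for is a legitimate choice in a phase 2 trial. This stands: the point is an efficiency recommendation only.

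**The gain rests on assumptions.** No AUC, R², score distribution or item prevalence is given. Two of the four levels of prediction yield nothing or a small loss. Gains of 4 to 5 points need an AUC near 0.70 among patients already selected on the score, for an outcome that includes low urine output. This also stands, and it is why the result is a range. Against it, the plan itself uses the score to pick high-risk patients and splits enrolled patients on it at 8, which suggests that it is expected to predict within the trial.

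**Differences below one point are hard to interpret.** The χ² test is discrete. Its exact type I error at 150 per arm is 4.9%, 5.3% and 5.7% for common AKI rates of 34%, 42% and 50%. Its exact power for 50% versus 34% is 81.3% at 150 per arm, and lies between 79.7% and 81.7% when one or two patients move between arms. So the none, weak and CMH results should be read as no material change, and no departure from 5% is claimed. The moderate gain is only slightly larger than this noise. The strong gain is well outside it.

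**The change needs more detail to be complete.** A patient can reach 6 points with one laboratory item absent, and Table 4 has no rule for that. A variance method is also needed, and eGFR enters both as a stratum and through the score. The first two are settled in the wording proposed below. The overlap is harmless: the covariates only need to predict the outcome, and in a randomised trial the standardised risk difference stays valid in large samples even if the working model, including linearity of the score, is wrong.

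**Conclusion.** The point holds as a worthwhile but optional-in-principle improvement: the trial is sound without it. The χ² test is valid and delivers the planned 80%. Adding the strata and the continuous risk score changes power by about −0.4 points at worst, +1.1 to +1.5 under moderate prediction and +4.0 to +4.8 under strong prediction. Nearly all of the gain comes from the score, and the strata alone add at most about 1 point. The size rests on assumed prognostic strength, Table 4 prevalences and site split, so confidence in it is medium. Confidence that adjustment does no material harm is higher, since type I error stayed close to 5%.

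**What to change.** Replace the primary analysis sentence in section 6.2, before unblinding, with wording such as:

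> The primary analysis is a logistic regression of AKI on treatment, site, eGFR stratum (<60 vs ≥60 ml/min/1.73 m²) and the AKI risk score as recorded at screening (continuous). The standardised (marginal) risk difference and risk ratio are reported with 95% confidence intervals. The primary P value is that of the standardised risk difference, with an influence-function (robust) variance. The unadjusted χ² test is a sensitivity analysis.

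Taking the score as recorded for eligibility means that no patient lacks a value, even if a component was unavailable. The standardised risk difference still compares the two proportions, so the treatment question does not change.

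As a minimum, use a CMH test stratified by site and eGFR. It respects the randomisation but gains little.

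The cost is SAP wording only. The covariates are already available at screening, and the sample size does not change.

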5. STUDY PROCEDURES

5.1 Drugs to be used

We will administer DFO or an equal volume of normal saline as an IV infusion over 12h. DFO will be administered at a total dose of 30 mg/kg (maximum total dose, 6g). The DFO (or normal saline) infusion will begin immediately prior to cardiac surgery (after induction of anesthesia and placement of a central venous catheter) and will be continued intra- and postoperatively for a total of 12h. The rationale for the dose of 30 mg/kg is provided in section 1.4. In preparing the DFO infusion, the research pharmacy at each site will follow similar methods used in prior DFO studies^{80,81} and according to the manufacturer recommendations: the prescribed amount of DFO powder, based on the patient's weight, will be dissolved in sterile water to achieve a concentration of 10%. The solution will then be further diluted in normal saline to achieve a final volume of 240mL to standardize the amount of fluid administered in both study arms. The DFO (or normal saline) will be delivered from the research pharmacy to the operating room by a member of the research pharmacy staff or a clinical research coordinator, and will be administered to the patient by the patient's nurse as a continuous 12h IV infusion through a central venous catheter. The DFO or normal saline infusion will begin immediately after induction of anesthesia and placement of a central venous catheter, which is typically inserted into an internal jugular or subclavian vein in the operating room 1 hour prior to the start of surgery for routine clinical care.

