5.2 Data to be collected

Upon enrollment, the following variables will be recorded: age; sex; race; ethnicity; comorbidities; home medications; type of surgery; urgency of surgery (elective, urgent, or emergent); and date of surgery. The following data will be recorded postoperatively:

- Cardiopulmonary bypass (CPB) time
- Aortic cross clamp time
- Estimated blood loss intraoperatively
- Requirement for (and number of) red blood cell transfusions intraoperatively and for 7d
- Requirement for (and volume) of Cell Saver used intraoperatively
- Duration of invasive mechanical ventilation
- Myocardial injury, atrial fibrillation, ARDS, and infection/sepsis within 7d
- Physiologic and vital sign data, including heart rate, blood pressure, and urine output for 7d
- Daily lab values, including hemoglobin and serum creatinine, for 7d
- Receipt of renal replacement therapy within 7d
- Reoperation during hospitalization
- ICU and hospital length of stay
- ICU and hospital mortality

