6.5 Statistical analysis for secondary endpoints

Hypothesis 2: DFO will attenuate peak postoperative increases in urinary markers of tubular injury (NGAL and KIM-1) and iron and oxidative stress, and will reduce the incidence of myocardial injury, atrial fibrillation, prolonged mechanical ventilation, and sepsis. For binary variables we will use the χ^2 test to compare the proportion of patients in each group who develop the endpoint. For continuous variables we will compare baseline (preoperative)-adjusted peak postoperative levels of each marker in DFO- versus placebo-treated patients using the two sample t-test or Wilcoxon rank-sum test depending on the distribution. We will also use a Generalized Estimating Equation for repeated measures to analyze longitudinal assessments of each marker in DFO- versus placebo-treated patients. For analyses of urinary tubular injury markers, we will perform sensitivity analyses using a global rank endpoint to account for anuria as a competing risk.^{101, 102} Finally, we will evaluate a composite endpoint of any renal or extrarenal acute organ injury or hospital mortality.

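### Section 6.2 treats CPB duration and intraoperative RBC transfusion as subgroups like baseline factors, although both are determined after study drug starts; they need a post-treatment label and a by-arm comparison

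*Combined protocol and SAP*

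**What the plan says.** Section 6.2 plans "logistic regression to assess for heterogeneity of therapeutic response to DFO across the following subgroups". The list that follows contains age, sex, race, preoperative eGFR, AKI risk score, "duration of CPB" (split at 120 min, and again at 120 and 180 min), then "intraoperative RBC transfusion; and type of surgery (elective vs. urgent/emergent"). Nothing in 6.2 separates these items by when they become known.

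Section 5.1 fixes the timing of study drug: the "infusion will begin immediately prior to cardiac surgery" and "will be continued intra- and postoperatively for a total of 12h". Section 5.2 draws the line that 6.2 does not. Type and urgency of surgery are recorded upon enrollment, whereas CPB time and "red blood cell transfusions intraoperatively and for 7d" come under the heading "The following data will be recorded postoperatively".

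Neither variable is an endpoint in section 6.4. Section 6.5 compares arms on the listed binary endpoints and, for continuous variables, on markers: "For continuous variables we will compare baseline (preoperative)-adjusted peak postoperative levels of each marker". No section plans a comparison of CPB time or transfusion between arms.

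**The concern.** Randomisation makes the arms comparable within strata fixed before treatment. Within strata formed during treatment, it does so only if DFO does not change which patients fall into them. If DFO altered the need for transfusion, for example, transfused patients on DFO and transfused patients on placebo would be different kinds of patient, and their AKI rates would differ without any drug effect on AKI. The plan neither states nor examines the condition that rules this out.

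These two variables also lie closest to the trial's hypothesis. Section 1.2.2 reports that longer CPB and more transfusions were each associated with higher catalytic iron. That links them to the disease pathway but does not show that DFO changes them. It does make a difference between their strata likely to be read as mechanistic support, with the same standing as a difference by eGFR. Section 8.2 says that positive findings would lay the basis for a phase 3 trial, and section 5.5 provides for an outside search for subgroups who may benefit. An unlabelled post-treatment signal could carry into either.

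**Working it through.** **The plan's own figure.** Section 6.3 gives 148 per group for 50% vs 34%, two-sided 0.05, 80% power. The pooled-variance formula without continuity correction gives 149 per group, and power at 148 is 79.9%. The sample size reproduces and is not in dispute.

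**Inputs.** From the documents: 50% AKI on placebo (6.3), 1:1 allocation (4.3), and 300 analyzable patients (6.6), hence n = 150 per arm. The documents give no transfusion rate, no CPB-time distribution and no DFO effect on either. Everything else below is assumed.

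**Transfusion model.** Let severity x be standard normal. AKI does not depend on arm: logit P(AKI|x) = bx, with b = 0.7, 1.0 or 1.5, so AKI is 50% in both arms. Transfusion on placebo: logit P(T|x) = a + bx, with a set to give 43%. DFO adds δ to this log-odds for everyone, for x > 0 only (sicker half), or for x ≤ 0 only (milder half), with δ set to give the chosen overall fall.

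- Share of an arm in stratum k: q = ∫P(T=k|x)φ(x)dx.
- AKI risk in that stratum: p = ∫P(AKI|x)P(T=k|x)φ(x)dx / q.
- R = OR(transfused) / OR(not transfused).
- SE² = sum over the four arm-by-stratum cells of 1/(nqp) + 1/(nq(1−p)).
- Rejection = Φ(−1.96 + ln R/SE) + Φ(−1.96 − ln R/SE).

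Example, b = 1.0, uniform 10-point fall (43% to 33%):

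- Not transfused: AKI 42.5% on placebo and 44.2% on DFO, OR 1.07.
- Transfused: 59.9% and 61.7%, OR 1.08.
- R = 1.01, SE = 0.49, rejection 5.0%.

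Both strata suggest slight harm although the true effect is null, but the interaction is almost undisturbed.

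| Fall in transfusion | Ratio of ORs (b = 0.7 to 1.5) | Interaction rejection at nominal 5% |
|---|---|---|
| None | 1.00 | 5.0% |
| 10 points, uniform | 1.00 to 1.02 (stratum ORs 1.04 to 1.15) | 5.0% |
| 10 points, sicker half only | 0.76 to 0.82 | 6.9% to 8.6% |
| 10 points, milder half only | 1.28 to 1.67 | 8.0% to 16.5% |
| 5 points, any pattern | 0.87 to 1.25 | at most 7.2% |
| 2 points, any pattern | 0.95 to 1.09 | at most 5.3% |

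The 16.5% requires transfusion in the milder half to fall from 20% to 0.1%. Simulation of the 10-point cases (40,000 trials each) agrees: 4.9% to 5.3% uniform, 6.9% to 8.6% sicker half, 8.0% to 16.3% milder half. These figures hold at a 43% baseline only. At 30% the milder half can contribute at most 5.3 to 9.6 points, so a milder-only 10-point fall is impossible there.

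**CPB time, below 120 vs 120 min or more.** Assumed lognormal, placebo median 100 to 140 min, log-SD 0.35 to 0.45, correlation with severity 0.3 to 0.5, same AKI model; 30% to 67% of patients are then at or above 120 min.

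| Shortening by DFO | Ratio of ORs | Rejection |
|---|---|---|
| 10%, uniform | 0.98 to 1.05 | 5.0% to 5.1% |
| 10%, sicker half only | 0.79 to 0.92 | at most 7.7% |
| 10%, milder half only | 1.08 to 1.26 | at most 7.5% |
| 5%, any pattern | 0.89 to 1.12 | at most 5.6% |

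The three-level CPB split was not computed.

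**What a by-arm comparison can show at 150 per arm.** For proportions, power = Φ{(|p₁−p₂|√n − 1.96√(2p̄(1−p̄))) / √(p₁(1−p₁)+p₂(1−p₂))}. For 43% vs 33%: (1.225 − 1.345)/0.683 = −0.18, power 43%. Over baselines of 30% to 60%, power is 14% to 16% for a 5-point fall and 41% to 52% for a 10-point fall. For log CPB time, power = Φ(|ln r|/(s√(2/150)) − 1.96), where r is the ratio of CPB times and s the log-SD. With r = 0.90 and s = 0.45: 0.1054/0.0520 = 2.03, power 53%. Over both log-SDs, power is 17% to 24% for a 5% shortening and 53% to 74% for 10%.

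**The case against.** The strongest reply is that section 6.2 tests heterogeneity, and a shift in these variables alone barely disturbs that test. The uniform rows show this. A false interaction needs a DFO effect on the variable that also differs by severity, plus a severity factor shared with AKI. The documents offer no evidence of any such effect. Clinicians are blinded (4.3), both arms receive the same 240 mL volume (5.1), and hypotension is called unlikely at this dose (7.2). The largest figures rest on extreme assumptions. No subgroup carries a confirmatory claim. Dropping the formal tests for these two variables also gives up the test nearest the iron-load rationale, when a caveat might do.

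Most of this stands, and it limits the size of the problem: this is a risk to interpretation and not a demonstrated bias. It does not remove the point. The within-stratum odds ratios, which any subgroup display shows, are distorted even by a uniform shift. Blinding limits differences in care but does not exclude a pharmacological effect. A general exploratory label, which 6.2 does not give, would not tell the reader which strata randomisation protects. The protocol uses the sounder approach elsewhere: in section 5.4, effect modification by monocyte markers is assessed on preoperative values. Losing the formal tests is a real but small cost, since the stratified results stay in the report.

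**Conclusion.** The concern holds. Section 6.2 mixes pre-treatment and post-treatment variables in one set of effect-modification tests, with no label and no by-arm check. The primary χ² test, the sample size and alpha are untouched.

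If DFO changes neither variable there is no bias. Under the assumptions above, with a null effect on AKI, false interaction rates stay at about 5% for uniform shifts and mostly below 9% for severity-dependent ones. They rise above that only when a 10-point fall in transfusion is confined to milder patients. The placebo transfusion rate, the CPB distribution and the severity slopes are all assumed, so these figures show scale and are not predictions. The change is worth making because it is cheap and these two subgroups are the most likely to be over-read.

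**What to change.** Amend section 6.2 as follows.

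1. Limit tests of effect modification to the listed variables fixed before study drug starts: age, sex, race, preoperative eGFR, AKI risk score and urgency of surgery.
2. Report CPB time and intraoperative RBC transfusion by arm, with confidence intervals for the differences.
3. Keep the AKI results stratified by these two variables, labelled descriptive, post-treatment and non-causal. Keep the label even if the by-arm comparison is non-significant: its power is low for shifts of this size, and equal proportions would not exclude different patient mixes.

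The cost is SAP wording and one table, since section 5.2 already collects both variables. The one loss is that the question closest to iron load becomes descriptive instead of a formal test.
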